8.2 SAFETY ASSESSMENTS

There are no known risks related to the study measures (Pure Tone Hearing Survey and questionnaires). The Intervention is being provided by UPMC Audiology and is provided elsewhere in the UPMC system. There have been no reported risks or adverse events related to the Consult or Engage Model of intervention. The Study Team will monitor all procedures and the DSMB will monitor the study as well. The DSC will visit each facility at each Test Time point to make sure all DCs are following the standard protocol for interacting with residents, enrolling residents, and collecting data.

8.3 ADVERSE EVENTS AND SERIOUS ADVERSE EVENTS

8.3.1 DEFINITION OF ADVERSE EVENTS

For this study, the following standard AE definitions are used:

Adverse event: Any unfavorable and unintended sign (including an abnormal laboratory finding), symptom, or disease temporally associated with the use of a medical treatment or procedure, regardless of whether it is considered related to the medical treatment or procedure.

Serious Adverse Event: Any AE that results in any of the following outcomes:

- Death
- Life-threatening
- Event requiring inpatient hospitalization or prolongation of existing hospitalization
- Persistent or significant disability/incapacity

8.3.2 DEFINITION OF SERIOUS ADVERSE EVENTS

There is no expectation of serious adverse events related to the research study. The research measures include a Pure Tone Hearing Survey and questionnaires. There is no expectation of a serious adverse event related to the intervention which includes typical hearing care.

8.3.3 CLASSIFICATION OF AN ADVERSE EVENT

8.3.3.1 SEVERITY OF EVENT

AEs will be collected and entered into the electronic data capture system.

AEs are graded using the Common Terminology Criteria for Adverse Events (CTCAE) according to the following scale:

Mild: Asymptomatic or mild symptoms; clinical or diagnostic observations only; intervention not indicated. An experience that is transient and requires no special treatment or intervention. The experience does not generally interfere with usual daily activities. This includes transient laboratory test alterations.

Moderate: Minimal, local or noninvasive intervention indicated; limiting age-appropriate instrumental ADL. An experience that is alleviated with simple therapeutic treatments. The experience impacts usual daily activities. Includes laboratory test alterations indicating injury, but without long-term risk.

Severe: Severe or medically significant but not immediately life-threatening; hospitalization or prolongation of hospitalization indicated; disabling; limiting self-care Activities of Daily Living (ADL). An experience that requires therapeutic intervention. The experience interrupts usual daily activities. If hospitalization (or prolongation of hospitalization) is required for treatment it becomes a SAE.

Life-threatening: Urgent intervention indicated

Fatal/Death: Death related to AE.

8.3.3.2 RELATIONSHIP TO STUDY INTERVENTION/EXPERIMENTAL MANIPULATION

The study uses the following AE attribution scale:

Unrelated: The AE is clearly not related to the study procedures (i.e., another cause of the event is most plausible, and/or a clinically plausible temporal sequence is inconsistent with the onset of the event).

Unlikely: The AE is likely not related to the study procedures (i.e., another cause of the event is plausible and/or a clinically plausible temporal sequence is inconsistent with the onset of the event) but causality cannot be clearly ruled out.

Reasonable Possibility: An event that follows a reasonable temporal sequence from the initiation of study procedures, but that could readily have been produced by a number of other factors.

Definite: The AE is clearly related to the study procedures.

AEs are identified through the Data Collectors who will be interacting with residents in the facilities. For Staff and Families, there is no direct interaction because they will be responding to surveys through mail or web link.

All SAEs and AEs will be recorded in the electronic data capture system immediately upon notification of the occurrence of the SAE or AE. If the event is deemed reportable (serious, unanticipated, and related), the AE will be reported per the IRB AE reporting.

SAEs and AEs related to study measures (considered very unlikely) will be reviewed by the Study Team to determine appropriate resolution. SAEs and AEs related to the intervention (considered very unlikely) will be reviewed by a licensed audiologist and UPMC risk manager for resolution.

8.3.3.3 EXPECTEDNESS

An Audiologist with appropriate expertise in hearing care will be responsible for determining whether an adverse event (AE) is expected or unexpected related to the intervention. An AE will be considered unexpected if the nature, severity, or frequency of the event is not consistent with the risk information previously described for the study procedures. This is a minimal risk study with no expected risks to participants.

8.3.4 TIME PERIOD AND FREQUENCY FOR EVENT ASSESSMENT AND FOLLOW-UP

All SAEs and AEs will be recorded in the electronic data capture system immediately upon notification of the occurrence of the SAE or AE. DCs will be responsible for recording this information. In addition, the DC will alert the DSC who will notify the PI. If the event is deemed reportable (serious, unanticipated, and related), the AE will be reported per the IRB AE reporting.

8.3.5 ADVERSE EVENT REPORTING

The study team does not anticipate any AEs due to the nature of the research activities. All AEs will be recorded in the electronic data capture system immediately upon notification of the occurrence of the SAE or AE. If the event is deemed reportable (serious, unanticipated, and related), the AE will be reported per the IRB AE reporting guidelines.

The Consult and Engage Interventions are care provided by UPMC staff and are not included in the IRB research activities. If there are Adverse Events related to these models of care, this would be reported in UPMC Risk Master and handled through UPMC protocols for adverse events related to clinical care.

Management of any AEs will be managed on a case-by-case basis and will be coordinated with the care team at the resident's facility if needed. AEs will be reported to the University of Pittsburgh IRB and PCORI within 10 days of the investigator first learning about the event. AEs will be included in DSMB reports.

8.3.6 SERIOUS ADVERSE EVENT REPORTING

In consultation with the PI, a trained member of the study team will be responsible for conducting an evaluation of a serious adverse event and shall report the results of such evaluation to the University of Pittsburgh IRB, PCORI, and the DSMB no later than 10 working days after the investigator first learns of the event.

8.3.7 REPORTING EVENTS TO PARTICIPANTS

N/A

8.3.8 EVENTS OF SPECIAL INTEREST

N/A

8.3.9 REPORTING OF PREGNANCY

N/A

8.4 UNANTICIPATED PROBLEMS

8.4.1 DEFINITION OF UNANTICIPATED PROBLEMS

Given the low risk of this project, unanticipated problems should be at a minimum. An unanticipated problem is any incident, experience, or outcome that is unexpected in terms of nature, severity, or frequency, given the intervention protocol and characteristics of the residents or staff.

The study team does not anticipate any UPs due to the nature of the research activities. The study procedures for residents consist of a Pure Tone Hearing Survey and two questionnaires completed in interview format. For staff and families, they will complete a short survey through the mail or internet. Note: The Consult and Engage Interventions are standard of care at UPMC and are not included in the IRB research activities. If there are UPs related to these models of care, this would be reported in UPMC Risk Master and handled through UPMC protocols for adverse events related to clinical care.

Management of any UPs will be managed on a case-by-case basis and will be coordinated by the PI with the care team at the resident's facility if needed.

8.4.2 REPORTING UNANTICIPATED PROBLEMS TO PARTICIPANTS

If any unanticipated problems occur, the Director of the facility will be notified and the PI and Data Survey Coordinator will work with the Director to determine the best way to disseminate information to residents. Depending on the unanticipated problem we may need to communicate with all residents, residents enrolled in the study, or only the resident directly impacted. These decisions will be made in consultation with the facility Director and the University of Pittsburgh IRB. Communication also may be directed at the family of the resident(s) depending on the issue.

Staff member who observes or is involved in the unanticipated problem will immediately notify PI [name] of a problem that involves a risk to residents or others (e.g. staff, residents, family).

PI [name] will report these unanticipated problems to the IRBs and PCORI within 48 hours.

9 STATISTICAL CONSIDERATIONS

9.1 STATISTICAL HYPOTHESES

- Primary Endpoint(s):

H_1

We hypothesize that Engage Model participants will have significantly greater satisfaction with participation in social activities across residents regardless of hearing status compared to those receiving the Consult Model.

H_0

There will be no difference in satisfaction with participation between participants in the Engage and Consult Model.

H_1

We hypothesize that Engage Model participants with hearing loss will have an increase in Hearing-Specific HRQoL compared to those receiving the Consult Model.

H_0

There will be no difference in Hearing-Specific HRQoL between participants with hearing loss in the Engage and Consult Model.

- Secondary Endpoint(s):

H_1

We hypothesize that Engage Model staff will have higher job satisfaction compared to staff in the Consult Model.

H_0

There will be no difference in job satisfaction between staff in the Engage and Consult Model.

H_1

We hypothesize that Engage Model family members will have reduced burden compared to staff in the Consult Model.

H_0

There will be no difference in family burden between staff in the Engage and Consult Model.

9.2 SAMPLE SIZE DETERMINATION

We used a method to estimate sample size that takes into account the cluster randomization, the stepped wedge design, and the longitudinal data on residents⁸⁴ (**RC-3**). Our study design originally included 8 clusters (facilities) with 5 time periods (including the baseline), 4 steps, 2 facilities switching from control to intervention at each step, and an average of 65 residents per facility

being continuously followed (**CI-2**). We expect some residents to leave the facility for different reasons and our design will allow new residents to contribute data from the time of moving into the facility until the end of the study period. We conducted sample size analyses accounting for intracluster correlation ($\rho=0.20$) (**RC-3**), individual autocorrelation ($\tau=0.5$), and cluster autocorrelation ($\pi=0.9$)⁸⁴. The *intracluster correlation* is a measure of correlation among residents measured at the same facility within the same time frame. Cluster randomized trials typically assume values between 0.01-0.10 with higher values indicating more similarity in outcomes within clusters such as schools, primary care clinics, or providers. We assumed a higher correlation given that residents are living within the same quarters and sharing the same residential experience. The *individual autocorrelation* is the correlation between any two measures within the same resident over time. We conservatively assumed this to be 0.5 as a lower bound because repeated measures within person are often highly correlated. The *cluster autocorrelation* is the correlation between two population means from the same cluster at different times. We assumed this would be very high (0.9) given the stability of the population in the facilities over time. This design achieves 80% power to detect the hypothesized effect size of 0.3 for either primary outcome (satisfaction with participation or hearing-specific health-related quality of life) between control and intervention periods (two-sided, $\alpha=0.025$ for each outcome). An effect size of 0.3 translates to a difference between groups of 3 points on the satisfaction with communication scale assuming a standard deviation between 9 and 10 based on our preliminary data from local facilities. An effect size of 0.3 translates to a difference between groups of 3.6 points on the hearing-specific health-related quality of life measure assuming a standard deviation of 12 based on our preliminary data from local facilities. These differences are considered clinically meaningful. We believe this hypothesized effect exists because of previous literature using these measures in clinical populations and from our pilot data.^{62,64}

The original sample size analysis for the study used a closed solution formula for a *closed* cohort design, fixed sample size per cluster, and an underlying model with assumptions valid for a large number of clusters. The study is an *open* cohort design allowing participants to drop out of the study (move out of the facility) and new residents to come into the study as they move into the facilities. In addition, the number of clusters is small (only 8) and the number of residents per facility is variable. We conducted simulations to assess the power and Type I error rate of our study given the open cohort design, variability in sample size across facilities, and statistical analysis model that accounts for the small number of clusters. We found the estimated power to be 77-79% with $\alpha=0.025$ and 85-87% with $\alpha=0.05$ with minimal to no inflation in the Type I error rates (observed 0.025 to 0.033 for $\alpha=0.025$ and 0.045 to 0.058 for $\alpha=0.05$) assuming a drop out (churn rate) of 7.5% per period. These simulations were sent to the DSMB and approved prior to study start. Once the study began, the targeted sample size per facility (~65) was deemed not to be achievable due to lower than expected census and higher than expected resident decline to participate. Additional simulations showed that with 10 facilities, 5 steps (2 facilities per step), and 30 residents per facility, we achieved 85% power for the same hypothesized effect size and correlation parameters.

9.3 POPULATIONS FOR ANALYSES

All enrolled residents will be included in the analyses. The Engage Model is a Facility and Individual Level intervention so all residents are potentially impacted by the intervention.

All staff and family members willing to participate will be included in the analysis.

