3 OBJECTIVES AND ENDPOINTS

OBJECTIVES	ENDPOINTS	JUSTIFICATION FOR ENDPOINTS
Primary		
Compare the effectiveness of a Consult Model versus an Engage Model in improving satisfaction with participation in social activities for all residents.	Satisfaction with Participation in Discretionary Social Activities – Short Form 7a V1.0	This is a measure with adequate psychometric data to support its use in identifying change in satisfaction with participation which is of primary interest when improving communication through hearing.
Compare the effectiveness of a Consult Model versus an Engage Model in increasing hearing-specific health-related quality of life (HRQoL) in residents with measured hearing loss.	Hearing Handicap Inventory for the Elderly (HHIE) – Screening V1.0	The HHIE is a reliable, valid measure of self-perceived hearing handicap. This is a direct measure of the intervention for individuals with hearing loss.
Secondary		
Compare the effectiveness of a Consult Model versus an Engage Model in increasing Staff Satisfaction.	Michigan Organizational Assessment Questionnaire (MOAQ)	This is a standardized measure of perceived stress by staff. Our previous stakeholders indicated that the staff questionnaire should be brief (3 questions).
Compare the effectiveness of a Consult Model versus an Engage Model in decreasing Family Burden.	Zarit Burden Interview - Modified 4 question V1.0	Reduction of burden is of interest in this study and the Zarit Burden Interview provides a standardized way to probe this outcome.

OBJECTIVES	ENDPOINTS	JUSTIFICATION FOR ENDPOINTS
Tertiary/Exploratory		
Define a threshold of improvement with exposure to the intervention	The HHIE and Satisfaction with Participation in Discretionary Social Activities will be used to assess threshold of improvement as a function of exposure to the Engage Model.	The two primary resident measures are of interest when defining a threshold or improvement over time.

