5 STUDY POPULATION

All residents in the 10 Assisted Living Facilities will be eligible to participate in the study. Every resident will be approached to participate. Residents who agree to be enrolled will participate in the Pure Tone Hearing Survey and the two questionnaires. All residents, regardless of enrollment in the study will be exposed to the intervention (Engage Model) because this intervention happens at both the individual and facility level.

One Family member for each resident will be invited to participate in the study. They will receive a link to an electronic version of the survey or will be mailed a paper version of the study with a self-addressed stamped envelope for return depending on their preference.

All Staff working in the facility will receive a paper version of the Job Satisfaction Survey so they can participate in the study.

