9.4 STATISTICAL ANALYSES

9.4.1 GENERAL APPROACH

Descriptive statistics will be used to characterize the overall cohort and each facility cohort for the variables of interest. Summary statistics will include means with standard deviations for normally distributed data and medians with interquartile ranges for skewed data. Categorical data will be summarized with frequencies and percentages. All tests will be two-sided and conducted at $\alpha=0.05$ and all confidence intervals calculated at 95% unless otherwise stated. All variables for the primary analyses are stated below. Although we will assess normality assumptions for the primary and secondary outcomes, we do not plan to use transformations for these scale outcomes due to lack of interpretability and the large sample size of the trial providing robustness to normality deviations in estimating and testing intervention effects. A full Statistical Analysis Plan is available as a separate document (HearCARE Statistical Analysis Plan, October 6, 2021).

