9.4.2 ANALYSIS OF THE PRIMARY ENDPOINT(S)

We will use linear mixed models to test the hypothesis of improving satisfaction with participation and hearing-specific HRQoL specifying the fixed effects of intervention and time and random effects for facility, facility*time, and resident (**RC-4**). These random effects are based on the statistical model referenced in Hooper (2016)⁸¹ that account for the correlation among individuals in the same cluster at the same time point, correlation between observations for the same individual at two time points, and the correlation between two means of the same cluster at two time points. Time will be treated as a categorical variable. We will estimate the mean difference and corresponding 95% confidence interval for the intervention effect (**IR-1**) and test that the difference between intervention and control conditions is significant. A two-sided test $\alpha=0.025$ for each outcome using a Wald t-test with Kenward Roger correction for small sample bias and Satterthwaite degrees of freedom will be employed. Primary analysis will be unadjusted for covariates.

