9.4.7 SUB-GROUP ANALYSES

In an effort to ascertain whether the intervention is more or less effective for certain resident subgroups (**RQ-4, HT-1**), we will explore the following groups (**HT-2**):

(a) those who have different degrees of hearing loss at baseline (~84% expected to have some level of hearing loss) and those who do not;

H_1 The intervention provided by the Engage Model and measured by the HHIE and Satisfaction with Participation will have more impact on residents with hearing loss at baseline as compared to residents with no measured hearing loss.

H_0 The intervention provided by the Engage Model and measured by the HHIE and Satisfaction with Participation will not have a different impact on residents with hearing loss at baseline as compared to residents with no measured hearing loss.

(b) those who have different degrees of hearing loss and use a device (~18-32% of 84%; note these are estimates and the actual percent of device use will be used) compared to those who do not use a device but have different degrees of hearing loss;

H_1 The intervention provided by the Engage Model and measured by the HHIE and Satisfaction with Participation will have more impact on residents with hearing loss who do not use a hearing device at baseline as compared to residents with hearing loss who do use a hearing device.

H_0 The intervention provided by the Engage Model and measured by the HHIE and Satisfaction with Participation will not have a different impact on residents with hearing loss who do not use a hearing device at baseline compared to residents with hearing loss who do use a hearing device.

(c) those with high social participation at baseline (~50%) and those with lower social participation;

H_1 The intervention provided by the Engage Model and measured by Social Participation will have more impact for residents with low social participation at baseline compared to residents with normal or high social participation.

H_0 The intervention provided by the Engage Model and measured by Social Participation will not have a different impact for residents with low social participation at baseline compared to residents with normal or high social participation.

(d) those with high hearing-specific HRQoL (~50%) and those with lower hearing-specific HRQoL. Scores of 0-8 on the HHIE are “low” and 10-40 are “high” with 10% indicating a significant change.⁸³

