H_1 The intervention provided by the Engage Model and measured by HHIE will have more impact for residents with high hearing-specific HRQoL at baseline as compared to residents with hearing-specific HRQoL within normal limits.

H_0 The intervention provided by the Engage Model and measured by HHIE will not have a different impact for residents with high hearing-specific HRQoL at baseline as compared to residents with hearing-specific HRQoL within normal limits.

The individual hearing threshold data will allow us to stratify according to hearing levels. We will use the ASHA classification of degrees of hearing loss (normal -10 to 15; slight 16 to 25; mild 26 to 40; moderate 41 to 55; moderately severe 56 to 70; severe 71 to 90; profound >91 dB).⁸⁴ The number of individuals in the HHIE subgroups and hearing level subgroups cannot be adequately estimated and will be known when data collection are complete. We will explore the heterogeneity using interaction terms (**HT-3**) between the factor of interest and the intervention fixed effect. Regardless of the significance, we will estimate the treatment effect for each subgroup with corresponding 95% confidence intervals (**HT-2**).

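### Section 9.3 puts every enrolled resident in the analyses, but Aim 2 and the primary HHIE hypotheses cover only residents with hearing loss

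*Combined protocol and SAP*

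**What the plan says.** Section 3 (Objectives and Endpoints) gives the second primary objective as improving "hearing-specific health-related quality of life (HRQoL) in residents with measured hearing loss". The first primary objective, on satisfaction with participation, is for all residents. Section 9.1 keeps the distinction. The satisfaction hypothesis applies whatever the resident's hearing status, while the HHIE null reads "There will be no difference in Hearing-Specific HRQoL between participants with hearing loss in the Engage and Consult Model", and its alternative has the same limit.

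Section 9.3, the only section on analysis populations, says "All enrolled residents will be included in the analyses". Its reason is that the intervention works at facility and individual level and so may affect everyone.

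Section 9.4.2 describes one model for both outcomes: "We will use linear mixed models to test the hypothesis of improving satisfaction with participation and hearing-specific HRQoL". It is unadjusted for covariates and names no population.

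Section 5 says "Residents who agree to be enrolled will participate in the Pure Tone Hearing Survey and the two questionnaires", so HHIE scores exist for residents with and without hearing loss. Section 9.4.1 adds that "A full Statistical Analysis Plan is available as a separate document"; that document was not available for this review.

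**The concern.** Both analyses can be run, and the text supports both. An analyst who follows 9.3 fits the HHIE model to all enrolled residents. One who traces 9.4.2 back to 9.1 restricts it to those with hearing loss. Each could claim to have followed the protocol, and the result is a primary test at two-sided alpha 0.025.

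The two analyses estimate different quantities unless the effect is the same in both groups. The plan itself expects a difference: in section 9.4.7 the intervention "will have more impact on residents with hearing loss at baseline as compared to residents with no measured hearing loss". It gives no size for that difference. If it exists, the all-resident estimate is pulled toward zero relative to the effect that Aim 2 asks about.

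The restriction also cannot be applied as the protocol stands. Section 8.1 collects thresholds at four frequencies in each ear, and section 9.4.7 lists grades ("normal -10 to 15; slight 16 to 25; mild 26 to 40", and upward). Nothing says which grade begins measured hearing loss, which frequencies are averaged, or which ear counts. Section 4.3 describes the expected 84% as having significant loss, and section 9.4.7 as having any level of loss, so the share does not settle the cut.

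**Working it through.** **Inputs from the protocol.** Section 9.2: effect size 0.3 SD (3.6 HHIE points at SD 12), two-sided alpha 0.025, intracluster correlation 0.20, cluster autocorrelation 0.9, individual autocorrelation 0.5, churn 7.5% per period, 10 facilities, 5 steps. Section 5.5: target 304 residents, and a census by facility totalling 507. Section 9.4.7: about 84% with hearing loss.

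**Assumptions.** The SD and the 84% share are the same in every facility and group. Facility sizes are proportional to the listed census, with large and small facilities paired, and results are averaged over all 120 step orders. Degrees of freedom are 30 to 44, where 44 = 60 facility-periods − 10 facilities − 6 periods.

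**Method.** Generalised least squares on facility-period means, with categorical time and an intervention term. For a facility of size m, with total variance 1:

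- variance of a period mean = 0.20 + 0.80/m
- covariance of two period means k periods apart = 0.20 × 0.9 + 0.80 × 0.5 × 0.925^k / m

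Power comes from the noncentral t distribution with noncentrality effect/SE.

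**Reproducing the plan's figures.**

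- Original design, 8 facilities of 65, no churn, 27 df (40 − 8 − 5): 80.2%, against 80% stated.
- Same design with 7.5% churn: 79.1% at alpha 0.025 (stated 77-79%) and 87.0% at alpha 0.05 (stated 85-87%).
- Current design, 10 facilities of 30, equal sizes, churn, 44 df: 87.3%. With sizes varying as in the census it is about 86%. Stated: 85%.

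The method agrees with the sponsor's simulations to within about 2 points.

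**Restricted HHIE test.** 0.84 × 304 = 255 residents, about 25 per facility. SE = 0.0908 SD. For 0.30 SD the noncentrality is 0.30/0.0908 = 3.30, and power is 82.2% (30 df) to 83.3% (44 df).

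**All-resident HHIE test.** SE = 0.0874 SD. If residents without loss gain a fraction f of the effect, the average effect is 0.30 × (0.84 + 0.16f).

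| f | Average effect (SD) | HHIE points | Power |
|---|---|---|---|
| 0 | 0.252 | 3.0 | 70-71% |
| 0.5 | 0.276 | 3.3 | 78-80% |
| 0.75 | 0.288 | 3.5 | 82-83% |
| 1 | 0.300 | 3.6 | 85-86% |

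**Break-even.** The two tests have equal power when 0.84 + 0.16f = 0.0874/0.0908, so f is about 0.76.

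**Sensitivity.**

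- The race totals in the baseline enrolment table (section 5.5) sum to 6 + 301 + 1 + 1 + 5 + 12 = 326. With 326 residents, the restricted test has 84-85% power. The all-resident test has 71-73%, 80-81% and 86-87% for f = 0, 0.5 and 1.
- With 304 residents and an assumed share of 90%, the restricted test has 83-85% and the all-resident test with f = 0 has 76-78%.
- With an assumed share of 70%, which the protocol does not suggest, the figures are 78-80% and 53-54%.
- Equal facility sizes raise each 304-resident figure by about 1 to 2 points.

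**The case against.** The best defence is that 9.3 is a general statement. Read with its stated reason, it guards against dropping residents because they had little exposure or no device, and may mean only that everyone enters some analysis. Section 9.4.2 says it tests the hypothesis, 9.1 defines that hypothesis for participants with hearing loss, and specific text can govern general text. Broad wording is also needed elsewhere, since the first subgroup analysis uses the HHIE in residents without loss. This reading is possible, but nothing in the protocol adopts it and 9.4.2 applies no filter.

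The separate analysis plan may settle both the population and the definition. If so, the protocol still needs to agree with it.

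On size, the defence has a point. Restricted power of 82-83% is above the original 80% target, and the gap from 85% is about as large as the spread between modelling choices. The 70-71% figure needs zero effect in residents without loss; the protocol says only that they gain less, and section 4.1 expects some spillover to untreated residents.

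Section 9.4.7 promises an estimate with a 95% interval in each subgroup, so an effect in residents with loss would be reported. It would be reported as exploratory, and does not replace the primary test.

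**Conclusion.** The concern holds. As written, 9.3 directs a primary test at alpha 0.025 to a population that differs from Aim 2 and from the HHIE hypotheses. That conclusion rests on the text alone.

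The numerical consequence depends on the unknown effect in residents without hearing loss. Against the restricted test, analysing everyone costs about 12 points of power if that effect is zero, makes no difference at about three quarters of the effect, and gains about 3 points if the effects are equal. These figures assume the planning correlations, a common SD, a hearing-loss share of 84% and 30 to 44 degrees of freedom. Because either choice can be the more powerful one, it should be fixed before outcome data are analysed.

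This should be corrected, but it does not threaten the feasibility of the trial. Confidence is medium because the separate analysis plan was not available.

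**What to change.** - **Section 9.3:** state the population by endpoint. Satisfaction with participation uses all enrolled residents. The primary HHIE analysis uses enrolled residents with measured hearing loss on the Pure Tone Hearing Survey at enrolment. Repeat this in 9.4.2 and make it agree with the separate analysis plan.
- **Definition:** before analysis, fix the dB cut, the frequency average, the better or worse ear, and how residents without a completed hearing survey are classed.
- **All-resident HHIE model:** keep it, labelled supportive. The subgroup comparison by hearing status can still use all residents.
- **Section 9.2:** re-run the existing simulation for the HHIE at the expected number with hearing loss (0.84 × 304 = 255, about 25 per facility; 0.84 × 326 = 274, about 27) and print the result.

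The cost is wording in two sections, one definition and one simulation re-run, with no extra data. Stated HHIE power will probably fall slightly, from 85% to about 82-83%. If residents without loss gain more than about three quarters of the effect, restricting the test gives up at most about 3 points of power.
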